5.4. Follow-up

The follow-up period will consist of virtual participant self-reporting of current symptoms, SpO2, and temperature via the platform, until they reach Day 90.

5.5. Efficacy Assessments

Determination of efficacy of the combination therapy, relative to placebo, will be determined as described in Section 1.4.

5.6. Safety Assessments

The study participants will provide daily self-assessments of symptom progression, using the platform. Body temperature, SpO2, and pulse will be measured and recorded by the participant daily, using Sponsor-provided thermometers and pulse oximeters, respectively. The study participants will perform a mobile ECG on Days 7 (\pm 1 day) and 14 (\pm 1 day) with the reads performed by the investigators, who will follow up with the participant.

Should the symptoms reported by the participant go outside of the normal ranges, severity, or expected condition, will trigger an alert to the site for the investigator to review for AEs/follow-up.

5.6.1. Demographic/Medical History

Participants will self-report demographic and medical history information through the platform.

5.6.2. Physical Examinations

No physical examinations will be conducted for this study.

5.6.3. Clinical Safety Laboratory Assessments

There will be mobile clinical laboratory samples taken and assessed for safety during this study. All subjects will have baseline and weekly comprehensive metabolic panels performed through Day 14 to assess eGFR and other hepatic and safety parameters.

5.6.4. Suicidal Ideation and Behavior Risk Monitoring

Based on the long history of the use of these medications, there is no expectation that there is an increased risk of suicidal ideation or behavior.

5.7. Adverse Events and Serious Adverse Events

The definitions of an AE or SAE can be found in **Appendix 2** of the Master Protocol (**LDOS-21-001**). CNS-related AEs including confusion, delirium, hallucinations, disorientation, agitation, seizures, and lethargy will be captured in the eCRF as an AE of special interest (AESI).

5.7.1. Time Period and Frequency for Collecting AE and SAE Information

All SAEs will be reported from the start of study interventions (Baseline) until the end of the follow-up period, at the time points specified in the SoA (Table 5). Medical occurrences that begin after obtaining informed consent, but before the start of study intervention will be recorded in the Medical History/Current Medical Conditions field in **Medical** not in the AE section.

All SAEs will be recorded and reported to the Sponsor or designee immediately, and under no circumstance should this exceed 24 hours, as indicated in **Appendix 2** of the Master Protocol (**LDOS-21-001**). The investigator will submit any updated SAE data to the Sponsor within 24 hours of it being available.

Investigators are not obligated to actively seek AE or SAE after conclusion of the study participation. However, if the Investigator learns of any SAE, including a death, at any time after a participant has been discharged from the study, and he/she considers the event to be reasonably related to the study intervention or study participation, the investigator must promptly notify the Sponsor. It is expected that, after the completion of the Follow-up period, that the study participant will be instructed to contact their personal physician to report any adverse events they may experience.

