Study Day		Day 1 Baseline/ Start of Treatment ⁴	Day 7(±1)	Day 14 (±1)	Day 30(±1) End of Treatment	Day 60	Day 90
Informed consent ⁵	Х						
Inclusion and Exclusion criteria	Х	Х					
Demographics	Х						
Medical History, including weight reporting ⁶	X						
Concomitant medication review	X	X	X	X	Х		
Blood draw for comprehensive metabolic panel (mobile phlebotomy & laboratory service)	Х		X	X			
Nasal swab for confirmatory PCR test for at-home antigen positive test prescreened participants (mobile phlebotomy & laboratory service)	X						
Randomization and initiation of drug shipment ⁷	Х						
Review of reported baseline symptoms		Х		X			
Confirmation of Study Drug Receipt & Initial Dose		X					
Confirmation of Study Drug Return Shipment ⁸					Х		
Review of eDiary for study drug compliance ⁹			X	X	Х		
Adverse Events Review		X	X	X	Х		
Participant Intake of study drug		Daily on Day	s 1–14				

Study Activities and Assessments	Screening & Randomization ¹		Treatment Po	eriod		Observati	on Period ²
Visit Number ³	1	2	3	4	5	6	7
Study Day		Day 1 Baseline/ Start of Treatment ⁴	Day 7(±1)	Day 14 (±1)	Day 30(±1) End of Treatment	Day 60	Day 90
Symptom questionnaires, spO2, and temperature		Daily for the entire treatment and observation period (Days 1–90)					
Mobile ECG		Х	Х	Х			

¹ Participant will complete demography, medical history, concomitant medications, and questions regarding inclusion and exclusion criteria [including results of SARS-CoV-2 PCR test and self-administered urine pregnancy test] via Site will review participant responses and confirm information with participant by Visit 2.

² During the observational period, while participant is not taking any IP, participant will record long term symptoms for Covid-19, but will be directed to consult with his/her primary care physician (PCP) for follow up of any health changes. Planned contacts with participants on Days 60 and 90 will be performed by study support staff only to confirm continued participation in the study.

³All participant visit activities will be performed remotely.

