1.4. Objectives and Endpoints

Study Description: This study (LDOS-21-001-02) is a virtual Phase 2 randomized, placebocontrolled, double-blind study to evaluate the safety and efficacy of the combination of famotidine and celecoxib as a PEP for newly-infected COVID-19 patients. This study is designed to test the efficacy and safety of combinations of two well-understood agents: famotidine and celecoxib. Each of these agents separately demonstrate clinical activity in mitigating COVID-19 disease symptoms or severity, and each of which appear to have separate and complementary mechanisms of action. Qualifying patients will have been confirmed COVID-19 – positive, and have symptoms of WHO Ordinal Scale levels \leq 3, and will be randomly assigned, in a 1:1 ratio, to one of two regimens, with 659 participants per group, as follows:

• **Group 1 (Study Product)**: 80 mg famotidine (PO) QID + celecoxib 400 mg first dose, followed by 200 mg (PO) BID for 5 days. Following this 5-day period, participants will continue their 80 mg famotidine QID treatment for an additional nine days.

• Group 2 (Reference Comparator): Matching Placebo for famotidine and celecoxib respectively, QID + BID for five days. Following this 5-day period, participants will continue to receive matching famotidine Placebo, QID, for an additional 9 days.

There will be a subsequent follow-up period of 90 days from Baseline.

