3.9. Dose Modification

Dose modification from the specified study regimens will be required if any of the following occur after the administration of study drugs:

- a participant's glomerular clearance (GFR) drops to <60 mL/min without developing QT prolongation or CNS AEs (i.e., delirium, hallucinations, disorientation, or seizures) after the results from their weekly laboratory results have been obtained by the investigator; or
- a QT wave prolongation is registered on their mobile ECG monitor; or
- a central nervous system (CNS) AE (i.e., delirium, hallucinations, disorientation, or seizures) is reported by the subject.

If any of the above occur, then the investigator will instruct the participant to stop all scheduled study medications.

For those participants with a drop in GFR and no QT prolongation or CNS AEs, they may resume study medications after testing demonstrates the GFR is >60 mL/min. Upon resolution, study drugs can be added back in stepwise fashion, e.g., BID, then TID, and finally QID. All missed or withheld doses will be noted in

For participants that had a QT prolongation or CNS AE (i.e., delirium, hallucinations, disorientation, or seizures), study medication will be permanently stopped and they will be followed for safety for the remainder of their study participation (Day 90).

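### SAEs are to be collected to Day 90 at the schedule's time points, but the schedule has no adverse event review after Day 30, so late ascertainment may be incomplete

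*Protocol*

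**What the plan says.** Section 5.7.1 sets the SAE window. Reporting starts with study intervention at Baseline and runs "until the end of the follow-up period, at the time points specified in the SoA", with Table 5 named as the schedule. Section 1.4 fixes the end of that window: "There will be a subsequent follow-up period of 90 days from Baseline".

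In Table 5 (Section 1.1), the row "Adverse Events Review" has an empty screening cell and then four marks, for Visits 2 to 5 (Days 1, 7, 14 and 30). Visits 6 and 7 (Days 60 and 90) have none. Footnote 2 describes those two visits: "Planned contacts with participants on Days 60 and 90 will be performed by study support staff only to confirm continued participation in the study". It also says that during this period the participant "will be directed to consult with his/her primary care physician (PCP) for follow up of any health changes".

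Section 5.4 describes follow-up in one sentence: "The follow-up period will consist of virtual participant self-reporting of current symptoms, SpO2, and temperature", through the platform to Day 90. It mentions neither AEs nor SAEs.

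**The concern.** Section 5.7.1 defers to Table 5 for the time points of SAE collection, and Table 5 supplies none in the last two months of the window. A site that follows the table has no instruction to ask about SAEs after Day 30. A site that follows the section text has a duty to Day 90. The two could collect different data.

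Incidence of related SAEs is the first secondary endpoint in Table 3, and Section 7.4.2 analyses incidence of death alongside the secondary safety endpoints. Neither is given a time window in those places. If the analysis runs to Day 90, a low count after Day 30 could mean few events or no enquiry, and the data could not tell the two apart.

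**Working it through.** No sample size, power or alpha figure bears on this point. The check is a comparison of texts and a count of days.

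**What the protocol requires or presumes up to Day 90**
- Section 5.7.1: SAEs are reported to the end of follow-up. The investigator is released from actively seeking events only once study participation has ended, and reporting to a personal physician is expected only after follow-up is complete.
- Section 5.7.5: pregnancies are collected to the end of follow-up.
- Section 3.9: participants permanently stopped for QT prolongation or a CNS event have safety follow-up to Day 90.

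**What is scheduled**

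| Visit | Day | AE review marked |
|---|---|---|
| 2 | 1 | yes |
| 3 | 7 (±1) | yes |
| 4 | 14 (±1) | yes |
| 5 | 30 (±1) | yes |
| 6 | 60 | no |
| 7 | 90 | no |

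Review is marked at 4 of the 6 visits from Day 1 onward, and at 0 of the 2 observation-period visits.

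**Length of the gap**
- 90 − 30 = 60 days. With the ±1 day window on Visit 5, it is 59 to 61 days.
- 60 / 90 = 67% of the SAE window has no scheduled enquiry.
- Planned dosing ends on Day 14, so the last review falls 30 − 14 = 16 days after the last planned dose, and the whole gap is off planned treatment.

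**Whether other text fills the gap**
- Table 5 has a daily row running to Day 90, but it covers symptom questionnaires, SpO2 and temperature, the same items as Section 5.4.
- Footnote 2 sends health changes to the participant's own physician from the start of the observation period. Section 5.7.1 foresees that route only after follow-up, about two months later.
- The Day 60 and Day 90 contacts are made by support staff, and no question about events is among their stated tasks.

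The mismatch is therefore not a single missing mark that other text repairs.

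**The case against.** The strongest reply is that collection does not stop at Day 30. The Data Collection paragraph of Section 1.1 lets participants report potential AEs on the platform every day throughout the study, follow-up included. Section 5.7.2 prefers open-ended screen prompts as the means of AE enquiry, so the platform, not a staff call, may be the intended instrument. Section 5.6 has abnormal symptom reports alert the site for AE review. Section 4.3 obliges the investigator or a designee to try to reach someone who repeatedly fails to enter data, which is what a hospitalised or deceased participant would do. AE methods are also delegated to Appendix 2 of the Master Protocol, which is not at hand.

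Much of this stands. A reader might infer that late SAEs and deaths will be under-counted, or that the 90-day safety follow-up is not delivered. The documents do not support either: several routes remain open, and 67% is a share of calendar days, not of events missed. Nor does footnote 2 forbid recording an SAE that a participant volunteers. The word *only* there may attach to the staff or to the purpose, and the 24-hour reporting duty in Section 5.7.1 would still apply.

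What does not stand is that these routes amount to collection at Table 5 time points. Platform reporting and alerts depend on the participant logging in, and a death cannot be self-reported. The stated content of the Section 4.3 contact is compliance and willingness to continue, not SAEs or vital status. The Master Protocol cannot settle the matter alone, because Section 5.7.1 ties the time points to this protocol's own table.

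**Conclusion.** The contradiction is real. Section 5.7.1 relies on Table 5 for SAE collection to Day 90, and Table 5, its footnote 2 and Section 5.4 provide no scheduled enquiry for the last 60 of the 90 days. The consequence is a risk of incomplete ascertainment of late SAEs, deaths and pregnancies. Its size in events cannot be worked out from the protocol.

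Three things limit the stakes. The primary endpoint, including its death component, closes at Day 30, within the period that has scheduled reviews, and is not affected. The gap begins 16 days after the last planned dose, which probably limits the number of treatment-related events at issue. The passive routes will catch some events.

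The conclusion assumes that Table 5 as printed is the operative schedule and that nothing in the Master Protocol adds an SAE enquiry at Days 60 and 90. The point merits correction because the protocol itself chose Day 90 and because the schedule decides which safety data will exist.

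**What to change.** 1. Add a row to Table 5 for SAE, vital status and pregnancy enquiry, marked at Days 60 and 90. It should be separate from the general AE review row, because Sections 5.7.1 and 5.7.5 extend only SAEs and pregnancies to the end of follow-up.
2. Use a brief open-ended, non-leading prompt at the contacts already planned, in keeping with Section 5.7.2, and pass any positive answer to the investigator.
3. Revise footnote 2 so that confirming participation is no longer the sole stated purpose of these contacts, and revise Section 5.4 to name the enquiry. Check Section 3.9 against the result.
4. State the time window for the related-SAE and death endpoints so that it agrees with the collection schedule.

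The cost is a short script and slightly longer contacts. No visit is added, and Section 3 already compensates participants for Days 60 and 90.

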Group 1	80 mg famotidine (PO) QID + celecoxib 400 mg first dose, followed by 200 mg (PO) BID for 5 days. Following this 5-day period, participants will continue their 80 mg famotidine QID treatment for an additional nine days.	659
Group 2	Matching Placebo for famotidine and celecoxib respectively – QID + BID for five days. Following this 5-day period, participants will continue to receive matching famotidine Placebo, QID, for an additional 9 days.	659

Table 4:Study Interventions

Disclosure Statement: This is a Phase 2 randomized, double-blind, placebo-controlled study to evaluate the safety and efficacy of the combination of famotidine and celecoxib as a post-exposure prophylaxis (PEP) for newly-infected for COVID-19 patients. These participants will not be hospitalized at enrollment, and all study activities will be performed at the participant's home. Investigational product and matching Placebo will be shipped directly to the participant from the Sponsor's supplier. There will be no other physical location where participants are seen. Virtual research teams will be organized by U.S. geographical region under the oversight of a Principal Investigator licensed to practice in the state(s) in which participants reside. Each site or group of affiliated sites will be required to designate at least one physical location to serve as a research facility for storage of any paper documents generated, mail correspondence or location

for inspection activity. This designated location will be listed as a research facility under Section #3 of Form FDA 1572.

Number of Participants: Approximately 1800 participants will be screened to achieve 1465 randomly assigned to study intervention and at least 1318 evaluable participants for an estimated total of 659 evaluable participants per group.

Study Design: The study design is shown schematically in Figure 1.

Schedule of Assessments: The participants will have responsibility for entering self-assessment of symptom severity, body temperature, blood oxygen concentration (spO2) using Sponsor-supplied devices, using the web-based platform. The study Schedule of Assessments is shown in Table 5.

LEAP-CT as a Post-exposure Prophylaxis for Newly-infected COVID-19 Patients

Version 2.0; 11 April 2022

Table 5:Schedule of Assessments

Study Activities and Assessments	Screening & Randomization ¹		Treatment	Period		Observ	ation Period ²
Visit Number ³	1	2	3	4	5	6	7

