⁴ Visit 1/participant informed consent must be performed within 5 days of a positive PCR or at-home antigen test, as per inclusion criteria. As IP will be shipped to the participant upon randomization, treatment start date (Visit 2/Day 1) may not occur until a few days after initiation of IP shipment. Participant will start treatment after IP receipt and review of inclusion/exclusion criteria with site. Date of first IP intake will always be considered Day 1, even if IP shipment is delayed outside of expected timeframe. If IP intake is delayed due to shipment, this will not be considered a protocol deviation.

⁵ Participant will complete Informed Consent Process via

⁶ Medical history should include relevant history from within the past 3 years, with inclusion of relevant medical events within the past 5 years.

⁷ IP will be shipped directly from drug depot to participants after randomization occurs within 2.

⁸ Participant will be provided return envelope for return of IP directly from participant to drug depot. At Visit 4, site will confirm with participant that he/she has shipped the IP back to the depot. Depot will be responsible for performing IP accountability.

⁹ Participant eDiary review will be performed by the clinical site staff.

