3.8. Concomitant Therapy

Any medication or vaccine (including over-the-counter or prescription medicines, vitamins, and/or herbal supplements) that the participant is receiving at the time of enrollment or receives during the study must be recorded along with:

- Reason for use
- Dates of administration including start and end dates
- Dosage instruction/prescription, including dose and frequency

The Medical Monitor should be contacted if there are any questions regarding concomitant or prior therapy.

Participants must abstain from taking prescription or nonprescription drugs (including vitamins and dietary or herbal supplements) within 1–3 days before the start of study intervention until completion of the follow-up visit, unless, in the opinion of the Investigator and Sponsor, the medication will not interfere with the study. Other concomitant medication may be considered on a case-by-case basis by the Investigator, in consultation with the Medical Monitor.

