7.3. Populations for Analyses

For purposes of analysis, populations are defined in Table 8.

Population	Description
Enrolled	All participants that have signed the Informed Consent Form, met the eligibility criteria, were randomized to study intervention, discontinued before first intake (Screening failures) or received at least one of study medication (Intent-To-Treat (ITT), Safety)
Full Analysis (FAS)	All participants who were randomized and received at least one dose of study medication. Participants in the FAS/ITT will be analyzed as randomized.

Table 8:Analysis Populations

Population	Description
Per Protocol (PP)	All participants who were included in the ITT, completed at least the 30-day assessments, and had no major protocol deviations that could have an influence on the primary efficacy endpoint. Participants in the PPS will be analyzed as treated.
Safety	All participants randomly assigned to study intervention and who take at least one dose of study intervention. Participants will be analyzed according to the intervention they actually received.

Participants excluded from the analysis sets mentioned above will be determined during the Blinded Data Review (BDR) and reasons for exclusions will be documented in the BDR report.

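### Serious events that begin between consent and first dose are filed as Medical History under Section 5.7.1 and fall outside its SAE reporting window, even when a study procedure or the required medication stop caused them

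*Protocol*

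**What the plan says.** Section 5.7.1 fixes the reporting window: "All SAEs will be reported from the start of study interventions (Baseline) until the end of the follow-up period". For the time before that it says: "Medical occurrences that begin after obtaining informed consent, but before the start of study intervention will be recorded in the Medical History/Current Medical Conditions" field, "not in the AE section". The section states no exception for seriousness or for relation to a study procedure.

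The start of the window is the first intake of study drug. Footnote 4 to Table 5 says: "Date of first IP intake will always be considered Day 1, even if IP shipment is delayed outside of expected timeframe". The same footnote allows that the "treatment start date (Visit 2/Day 1) may not occur until a few days after initiation of IP shipment".

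Section 3.8 requires participants to abstain from other drugs "within 1–3 days before the start of study intervention until completion of the follow-up visit", unless the Investigator and Sponsor judge that a drug will not interfere with the study.

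Table 8 (Section 7.3) counts among the enrolled those randomised who "discontinued before first intake (Screening failures"), and defines the Safety population by at least one dose. The Synopsis gives the planned numbers: "Approximately 1800 participants will be screened to achieve 1465 randomly assigned to study intervention and at least 1318 evaluable participants".

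**The concern.** The interval that Section 5.7.1 sends to Medical History is one in which the protocol itself acts on participants. Blood is drawn, some participants are swabbed, everyone eligible is randomised, and some must begin to go without drugs they were taking. Serious harm from any of these steps is harm from trial participation, but the rule records it as if it were a pre-existing condition.

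The stake is patient safety and oversight. Under Section 5.7.1 such an event does not enter the 24-hour SAE route. If it prevents dosing, the participant leaves as a screen failure and is absent from the safety tables too. The Sponsor and the DSMB could then lack a systematic record of harm from the screening steps and the medication stop.

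**Working it through.** This is mainly a check of text. The only arithmetic is a count of people.

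**1. What happens before first dose.** Section 5.1 lists, after consent, a metabolic panel by mobile phlebotomy, a nasal swab for those with only a positive antigen test, then randomisation and drug shipment. Section 3.8 starts the medication stop 1–3 days before first dose. Exclusions 4 and 5 make eligibility depend on whether certain treatments can be paused during the study. Table 5 first marks the adverse event review at Visit 2/Day 1, which agrees with Section 5.7.1. The lag from shipment to first dose is described as a few days, with no upper limit.

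**2. How the same harm is treated, by time of onset.**

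| Onset of a serious event related to a procedure or to the medication stop | Treatment under Section 5.7.1 |
|---|---|
| Consent to first dose | Medical History; outside the SAE window |
| First dose to end of follow-up (Day 90) | Reportable as an SAE whatever the cause; covers the Day 7 and Day 14 blood draws and the continuing medication stop |
| Learned of after discharge from the study | Must be notified if judged reasonably related to study intervention or participation |

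The gap is the first row only. The third row shows that the section accepts harm from participation alone as notifiable, which sits oddly with the first.

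**3. Participants who are never dosed.** Section 5.2 sends anyone found ineligible at Baseline out as a screen failure. Without a first dose the SAE window never opens, and Table 8 keeps the person out of the Safety population.

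**4. Planned size of that group.**
- Inputs: 1465 randomised and at least 1318 evaluable (Synopsis, Number of Participants); a 10% screen failure rate (Section 7.2).
- The plan's own step: 1318 / 0.90 = 1464.4, rounded up to 1465. This reproduces the stated figure.
- Randomised but not evaluable: 1465 − 1318 = 147, and 147 / 1465 = 10.0%.
- Link to dosing: Section 7.2 places evaluable participants in the Full Analysis population, and Table 8 defines that population as randomised with at least one dose. On these definitions the 147 are randomised and not dosed.

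**5. What cannot be computed.** The Synopsis implies 1800 − 1465 = 335 people screened but not randomised. The documents do not say how many of them sign consent and reach a blood draw or swab. They give no rate of serious events before dosing, and they put no limit on the length of the interval.

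**The case against.** **A reader might infer that harm from study procedures or the medication stop is never reported as an SAE.** The text does not support that. From first dose onward every SAE is reportable regardless of cause, and the post-discharge clause may catch some earlier events. The point is confined to events that begin before dosing.

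**Master Protocol Appendix 2 is not among the documents.** It holds the AE and SAE definitions and the reporting procedures, and it may contain a consent-onward rule for procedure-related events. This stands as a limit: what can be shown is a gap in Section 5.7.1, not in the whole safety system. But Section 5.7.1 itself sets the collection window, so if Appendix 2 differs, sites hold conflicting instructions and the sentence still needs work.

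**Another route exists.** Section 5 asks that immediate safety concerns be discussed with the Sponsor at once, with no start at first dose. That is fair, but it is framed around whether study intervention should continue, and it is not SAE reporting.

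**The medication-stop route is narrow.** Exclusion 5 mentions antiarrhythmics, but exclusion 10c bars a history of arrhythmia and other cardiovascular disease, so few such users could enter. Section 3.8 waives the stop for non-interfering drugs and places only 1–3 days of it before dosing. All of this stands. It reduces the likely number of events but does not remove the gap.

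**A reader might take 1800 − 1318 = 482, or 27% of those screened, as the number exposed.** That assumes everyone screened underwent study procedures. Section 8.1.3 has the Investigator judge people potentially qualified before consent is administered, and the swab applies only to antigen-positive participants. The 482 should not be used.

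**A reader might also infer that an event beginning before dosing and worsening on treatment is lost as baseline.** Section 5.7.1 governs where the event is first recorded. Whether later worsening counts as an AE is a matter of definition, which the protocol leaves to Appendix 2.

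**Conclusion.** The point holds for one window: serious events that begin after consent and before first dose. As Section 5.7.1 is written, those caused by the screening blood draw, the confirmatory swab or the start of the medication stop go to Medical History. In participants who are never dosed they are outside the Safety set as well.

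In size, about 147 of 1465 randomised participants (10%) could pass through this interval without ever entering the SAE window. This assumes that evaluable means dosed and that the planned numbers are met. It counts people without a reporting window, not events; the number of events is unknown and may be small. How many non-randomised people are affected is not given.

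The arm comparison is not biased: the interval precedes any study drug in both arms of a double-blind trial. No sample size or error rate changes. This is a gap in safety reporting that is worth closing because closing it costs little, subject to what Master Protocol Appendix 2 says.

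**What to change.** Add one exception to Section 5.7.1: from signature of the ICF, any serious event judged related to a study procedure or to a protocol-required change in existing medication is recorded as an SAE and reported within 24 hours, whether or not study drug is later taken. Unrelated events before dosing can stay in Medical History.

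List these events for all consented participants, not only the Safety set, and include the listing in the DSMB package. Reconcile the wording with Master Protocol Appendix 2 so that sites have one rule.

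Cost: one sentence, one relatedness flag in the eCRF, one extra listing and possibly a few additional SAE reports. No visit or procedure is added.
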